Caregiver Strain Index (CSI)		X		X			X			X			X

RED=Primary and Secondary Outcomes, BLACK=Additional Assessments by Stroke Mobile

SRU=UAB's Survey Research Unit

¹Complications monitored: Urinary tract infection, pneumonia, aspiration, deep vein thrombosis, skin breakdown, fall, myocardial infarction, depression, fever/other infection, and Afib.

²Risk factor profile: hypertension, diabetes, hyperlipidemia, smoking status, BMI, CHADS2VASC score, CRP, Afib, family history.

*Will be collected if patient/caregiver are able and/or available.

Table 8. Data Monitoring Paradigm: ISPU Arm, Stroke Mobile Visits 1-12

Item/Metric	In Hospital Prior to Discharge	Post Discharge Visit to Home/Facility											
		Day 0-14	Month of Visit										
			1	2	3	4	5	6	7	8	9	10	11
Glasgow Coma Scale (GCS)*	X												
Barthel Index*	X	X					X						X
Stroke education*	X	X	X	X	X	X	X	X	X	X	X	X	X
PT/OT/ST visits scheduled*	X												
Patient Medical History	X												
4-item Medication Adherence Scale*		X					X			X			X
Hill-Bone Compliance*		X					X						X
Epworth Sleepiness Scale*		X					X						X
Montreal Cognitive Assessment (MoCA)*		X					X						X
Frenchay Activities Index*		X					X						X
Antiplatelet use assessed, if appropriate*		X	X	X	X	X	X	X	X	X	X	X	X
Anticoagulant use assessed, if appropriate*		X	X	X	X	X	X	X	X	X	X	X	X
INR at-target, if appropriate*		X	X	X	X	X	X	X	X	X	X	X	X
Antihypertensive assessed, on intervention*		X	X	X	X	X	X	X	X	X	X	X	X
Antihypertensive assessed, at target*		X	X	X	X	X	X	X	X	X	X	X	X
Statin assessed, on intervention*		X	X	X	X	X	X	X	X	X	X	X	X
Hyperglycemia assessed, on intervention*		X	X	X	X	X	X	X	X	X	X	X	X
Hyperglycemia assessed, at target*		X		X			X						X
Smoking Cessation: On intervention, At target*		X	X	X	X	X	X	X	X	X	X	X	X
BMI: Discussed, at target*		X	X	X	X	X	X	X	X	X	X	X	X
Diet: Discussed, at target*		X	X	X	X	X	X	X	X	X	X	X	X
Exercise: Discussed, At target*		X	X	X	X	X	X	X	X	X	X	X	X
DVT assessed*		X	X	X	X	X	X	X	X	X	X	X	X
Skin assessed*		X	X	X	X	X	X	X	X	X	X	X	X
Mobility assessment* ¹		X					X						X
Depression intervention, if needed*		X	X	X	X	X	X	X	X	X	X	X	X
Caregiver Intervention, if needed*		X	X	X	X	X	X	X	X	X	X	X	X
Document tele- or phone consult to Stroke Central*		X	X	X	X	X	X	X	X	X	X	X	X
Stroke Mobile Team Conference attendance (monthly)*		X	X	X	X	X	X	X	X	X	X	X	X
Stroke Central Check-in with Stroke Mobile (daily)*		X	X	X	X	X	X	X	X	X	X	X	X
Establish plans for post intervention follow-up*													X

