Self-reported Assessment of Life’s Simple Seven*		X											X
SRU=UAB’s Survey Research Unit													
¹Mobility Assessment includes: Berg Balance Test, Functional Reach Test, Timed Up and Go.													
*Will be collected if patient/caregiver are able and/or available.													

Intervention Discontinuation Evaluations. If the patient or caregiver/family declines follow up in-person visits, we will offer follow-up phone or virtual evaluations for primary and secondary outcomes and other assessments. If consent not provided for this, no follow up will occur.

Special Instructions and Definitions of Evaluations. Evaluations to be performed include: SIS and smRS, NIHSS, GCS, 4-item Medication Adherence, medication side effects, Hill Bone Compliance, Frenchay, MoCA, Barthel's Index, Epworth Sleepiness Scale, PHQ-9 depression scale, Caregiver Strain Index, blood pressure, Cholesterol panel, Hemoglobin A1c, INR (as appropriate), BMI, Smoking cessation, exercise assessment, diet assessment, readmission, recurrence, bleeding assessment and INR assessment (see Tables 7 and 8).

Final On-Study Evaluations. On study evaluations will be completed by Stroke Mobile and the University of Alabama Birmingham (UAB) SDCC Survey Research Unit (SRU) to include SIS and smRS and other assessments (see Table 5).

Concomitant Interventions. None.

Study Intervention Modifications. None.

Assessments. Tables 7 and 8 identify and define the assessments and the timeframe for each measurement parameter.

Other Laboratory Studies. None.

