8. STUDY MONITORING

A. Data and Safety Monitoring Board (DSMB)

A formal Data and Safety Monitoring Board (DSMB) will be convened at regular intervals (for example, twice a year) to review recruitment, data security, and patient safety. We do not anticipate adverse events from this intervention, but the DSMB will monitor overall outcomes, including the following: death, recurrent stroke, rehospitalization, serious hemorrhage, recurrent or new ischemic event, serious adverse experiences, and premature withdrawal from the study. This study does not involve agents that likely will be associated with adverse experiences; as such, the DSMB will have a follow-up schedule and Significant Adverse Effects (SAE) reporting schedule that will include regular meetings with possible emergency meetings.

Data and Safety Monitoring Plan. The DSMB is tasked with mandating specific data required for independent analysis. A formal DSMB Plan will be developed by the DSMB Chair and the CCC and SDCC PIs that includes a framework for monitoring of study data and process, clinical and primary/secondary outcomes and will be submitted to the full DSMB. The frequency of data and safety monitoring will be determined in consultation with PCORI.

B. Adjudication Committee (AC)

In addition to the PI, two vascular neurologists will be charged with adjudicating stroke-related hospitalizations reported during the follow up period. This group (the Adjudication Committee) will review specific outcomes, including recurrent stroke, including subtype; and serious hemorrhage, including site.

C. Criteria for Intervention Discontinuation

- Revocation of informed consent.
- Subjects moving substantial distance from the original geographical location.
- Morbidity or mortality giving rise to insurmountable barriers to continued assessment.

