
RED=Primary and Secondary Outcomes, BLACK=Additional Assessments by Data Coordinator SRU=UAB's Survey Research Unit ¹Complications monitored: Urinary tract infection, pneumonia, aspiration, deep vein thrombosis, skin breakdown, fall, myocardial infarction, depression, fever/other infection, and Afib. ²Risk factor profile: hypertension, diabetes, hyperlipidemia, smoking status, BMI, Afib, family history. *Will be collected if patient/caregiver are able and/or available.
													

Intervention Discontinuation Evaluations. If the patient or caregiver/family declines follow up in-person visits, we will offer follow-up phone or virtual evaluations for primary and secondary outcomes and other assessments. If consent not provided for this, no follow up will occur.

Special Instructions and Definitions of Evaluations. Evaluations to be performed include: SIS and smRS, PHQ-9 depression scale, Caregiver Strain Index, blood pressure, Cholesterol panel, Hemoglobin A1c, BMI, Smoking cessation, exercise assessment, diet assessment, readmission, and recurrence, and others (see Table 7).

Final On-Study Evaluations. On study evaluations will be completed by the Coordinator and the University of Alabama Birmingham (UAB) SDCC Survey Research Unit (SRU) to include SIS and smRS, and other assessments (see Table 5).

Concomitant Interventions. None.

Study Intervention Modifications. None.

Assessments. Table 7 identifies and defines the assessments and the timeframe for each measurement parameter.

Other Laboratory Studies. None.

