8. INTERVENTION DISCONTINUATION

A. Data and Safety Monitoring Board (DSMB)

A formal Data and Safety Monitoring Board (DSMB) will be convened at regular intervals (for example, twice a year) to review recruitment, data security, and patient safety. We do not anticipate adverse events from this intervention, but the DSMB will monitor overall outcomes, including the following: death, recurrent stroke, rehospitalization, serious hemorrhage, recurrent or new ischemic event, serious adverse experiences, and premature withdrawal from the study. This study does not involve agents that likely will be associated with adverse experiences; as such, the DSMB will have a follow-up schedule and Significant Adverse Effects (SAE) reporting schedule that will include regular meetings with possible emergency meetings.

Data and Safety Monitoring Plan. The DSMB is tasked with mandating specific data required for independent analysis. A formal DSMB Plan will be developed by the DSMB Chair and the CCC and SDCC PIs that includes a framework for monitoring of study data and process, clinical and primary/secondary outcomes and will be submitted to the full DSMB. The frequency of data and safety monitoring will be determined in consultation with PCORI.

B. Adjudication Committee (AC)

In addition to the PI, two vascular neurologists will be charged with adjudicating stroke-related hospitalizations reported during the follow up period. This group (the Adjudication Committee) will review specific outcomes, including recurrent stroke, including subtype; and serious hemorrhage, including site.

C. Criteria for Intervention Discontinuation

- Revocation of informed consent.
- Subjects moving substantial distance from the original geographical location.
- Morbidity or mortality giving rise to insurmountable barriers to continued assessment.

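### Bleeding assessment is named for ISPU only and the adjudication intake rule is unclear, so serious hemorrhage is at risk of unequal ascertainment between arms

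*Protocol*

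**What the plan says.** The protocol comes in an ISPU version and a CSC/PSC version.

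- **ISPU, section 6.A, list of evaluations.** Medication side effects appear in the list, which ends "readmission, recurrence, bleeding assessment and INR assessment (see Tables 7 and 8".
- **CSC/PSC, section 6.A, list of evaluations.** The list ends "exercise assessment, diet assessment, readmission, and recurrence, and others (see Table 7". It names no bleeding, side-effect or INR item.
- **Complications footnote to Table 7, both versions.** The list is the same in each and closes with "skin breakdown, fall, myocardial infarction, depression, fever/other infection, and Afib". Bleeding is not in it.
- **Section 8.A, both versions.** The DSMB is to monitor "death, recurrent stroke, rehospitalization, serious hemorrhage, recurrent or new ischemic event", among other events. In the CSC/PSC version, section 8 carries a different title but the same text.
- **Section 8.B, both versions.** In addition to the PI, "two vascular neurologists will be charged with adjudicating stroke-related hospitalizations reported during the follow up period". The next sentence says that the committee reviews "recurrent stroke, including subtype; and serious hemorrhage, including site".
- **SAP.** Sections 1 and 4 list mortality, recurrent stroke, rehospitalization and other secondary outcomes. Hemorrhage is not among them, and it is not a primary or secondary outcome in protocol section 1.B either.

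**The concern.** A safety count can be compared between arms only if the event is looked for in the same way in each. Here a bleeding item is named for one arm and not for the other. The ISPU arm also has far more scheduled contacts at which a bleed could come to light. ISPU staff record antiplatelet, anticoagulant and INR status at those contacts, and the SAP presumes that ISPU works partly through lower systolic pressure, so it is reasonable to want a clean count of bleeding.

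If more hemorrhages were recorded under ISPU, the DSMB could not tell closer questioning from harm. If the counts were equal, better detection in one arm could be hiding a difference. Separately, the committee's intake and its review list do not match, so it is unclear whether a serious bleed outside the brain would be sent to it.

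**Working it through.** The documents give no hemorrhage figure to reproduce, so the check sets the two versions side by side and then gives an illustration on assumed inputs.

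**1. Where bleeding is collected**

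| Item | ISPU | CSC/PSC |
|---|---|---|
| Bleeding assessment in the 6.A list | named | not named; the list is open-ended and points to Table 7 |
| Bleeding row in the data tables | none in Table 7 or 8 | none in Table 7 |
| Bleeding in the complications footnote | no | no |
| Antiplatelet, anticoagulant and INR rows | Table 8, 12 post-discharge marks each | none |
| Readmission surveillance marks (Table 7) | 12 | 3 |
| General adverse-event route to the DSMB (section 10.B) | yes | yes, same text |

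Two points follow. The ISPU bleeding assessment has no visit or form assigned, although the tables are meant to define each assessment. The Table 8 rows record drug use and INR control, where appropriate and where the patient is able. They are not questions about bleeding and should not be counted as such.

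**2. Contact frequency.** The ratio is 12 / 3 = 4.0. The 12 agrees with the 12 in-home visits in section 10.A of the ISPU version, and the 3 with the research visits at 3, 6 and 12 months in section 5 of the CSC/PSC version. A control patient must therefore recall an event over 3 months (0 to 3 and 3 to 6) or 6 months (6 to 12).

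**3. Adjudication.** The charge in 8.B is stroke-related hospitalizations. The review list in 8.B includes serious hemorrhage with its site, separately from recurrent stroke. Table 1 adds that records are collected where needed for committee review. In the extracted text this sits beside the mortality, recurrent stroke and rehospitalization rows, but the cell layout is broken and its span is inferred. None of the three states whether a hospitalization for a non-stroke bleed is referred, and serious hemorrhage is not defined.

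**4. Illustration of size.** All detection and risk values are assumptions. The protocol's reduced total of 1,262, split equally (also assumed), gives n = 1,262 / 2 = 631 per arm. True risk is the same in both arms.

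- Recorded events = n × risk × detection probability.
- Recorded ratio = ISPU detection / CSC/PSC detection, with ISPU detection set at 0.95.

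| CSC/PSC detection | Recorded ratio | Recorded events at 2% risk (ISPU vs CSC/PSC) |
|---|---|---|
| 0.95 | 0.95/0.95 = 1.00 | 12.0 vs 12.0 |
| 0.80 | 0.95/0.80 = 1.19 | 12.0 vs 10.1 |
| 0.60 | 0.95/0.60 = 1.58 | 12.0 vs 7.6 |

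For example, 631 × 0.02 × 0.95 = 12.0 and 631 × 0.02 × 0.60 = 7.6.

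The chance that a two-sided 5% comparison of proportions comes out falsely significant against ISPU (nominally 2.5% in that direction) is as follows:

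| CSC/PSC detection | 1% risk | 2% risk | 4% risk |
|---|---|---|---|
| 0.80 | 4.7% | 6.0% | 8.4% |
| 0.60 | 10.5% | 17.0% | 30.0% |

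These use a normal approximation and ignore clustering by site, so they show direction and rough order only.

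**The case against.** The case for leaving the plan alone has several parts, and most of them limit the point.

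- **Other routes exist in both arms.** Mortality, recurrence and readmission surveillance and the general adverse-event route apply to everyone. A hemorrhagic stroke can enter through recurrence surveillance, and its subtype is adjudicated. This stands. It confines the problem mainly to bleeds without admission, and to admissions forgotten over the longer recall interval. A reader might infer that hemorrhage is in fact counted unequally; the documents establish only the risk.
- **Adjudication may cover non-stroke bleeds.** A reader might infer that these can never reach the committee. The review sentence in 8.B and the records route in Table 1 do not support that. It is also possible that site means location within the head. What stands is that the text leaves referral unsettled.
- **The ISPU bleeding item may be nominal.** With no row in Tables 7 or 8, it may not be asked systematically. This weakens the claim of a working asymmetry, but it leaves one arm told to assess bleeding and the other not.
- **The DSMB can require its own data.** Section 8.A allows this and refers to a separate DSMB Plan that is not among the documents. That plan may solve the problem. It could not, however, compare an item collected in one arm only.
- **Hemorrhage is not a prespecified outcome.** This is correct, so its absence from SAP section 4.1 is not an omission from the plan.
- **It may be late.** The SAP says that 21 sites provided data, which suggests that collection is advanced or finished. A new form item would then reach few patients or none.

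**Conclusion.** The point holds as a risk to safety monitoring. Bleeding assessment is named for ISPU alone and tied to no table row in either arm. ISPU has four times as many readmission surveillance contacts. The intake and review wording of 8.B must be reconciled. Following the plan as written would leave a harm that the DSMB monitors prompted in one arm only.

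The size is unknown. The ratios of 1.00 to 1.58 rest entirely on assumed detection probabilities, and equal detection would mean no bias at all. The gap should be smallest for hemorrhages that led to admission or death. The documents do not support a claim that ISPU will show excess bleeding, or that no usable comparison can be made. No efficacy endpoint and no analysis in the SAP is affected.

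**What to change.** 1. **Collection.** Ask one hemorrhage item (date, anatomical site, hospitalized yes or no) at 3, 6 and 12 months in both arms, in identical words, for participants still in follow-up. Add a row for it to Table 7 in both versions. The blinded telephone survey already reaches both arms at those times and is one place to put it.
2. **Comparison.** Base any between-arm hemorrhage count on events leading to hospitalization or death, ascertained at those common time points. Define serious hemorrhage accordingly for this purpose, and report that ascertainment otherwise differed by arm.
3. **Adjudication.** In 8.B of both versions, set the intake as stroke-related hospitalizations plus any hospitalization or death with hemorrhage. Remove arm and clinical-site identity from the packets.

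The cost is one form item at existing contacts, a wording change in 8.B and a few more packets for the committee. The downside is that bleeds without hospitalization leave the comparison. If data collection has closed, item 1 falls away. The definition, the intake rule and the stated limitation can still be applied to readmission and death records. Adding hemorrhage to SAP section 4.1 on this definition is optional.

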7. MANAGEMENT OF ADVERSE EXPERIENCES

Adverse experiences are anticipated to be rare. This study does not involve agents or interventions that are likely to be associated with adverse experiences. This study will use the standardized JC and ASA national guidelines for stroke care management. As revisions occur to the national guidelines these will be made available to clinical sites to modify their clinical site stroke patient care management strategies.

8. STUDY MONITORING

A. Data and Safety Monitoring Board (DSMB)

A formal Data and Safety Monitoring Board (DSMB) will be convened at regular intervals (for example, twice a year) to review recruitment, data security, and patient safety. We do not anticipate adverse events from this intervention, but the DSMB will monitor overall outcomes, including the following: death, recurrent stroke, rehospitalization, serious hemorrhage, recurrent or new ischemic event, serious adverse experiences, and premature withdrawal from the study. This study does not involve agents that likely will be associated with adverse experiences; as such, the DSMB will have a follow-up schedule and Significant Adverse Effects (SAE) reporting schedule that will include regular meetings with possible emergency meetings.

Data and Safety Monitoring Plan. The DSMB is tasked with mandating specific data required for independent analysis. A formal DSMB Plan will be developed by the DSMB Chair and the CCC and SDCC PIs that includes a framework for monitoring of study data and process, clinical and primary/secondary outcomes and will be submitted to the full DSMB. The frequency of data and safety monitoring will be determined in consultation with PCORI.

B. Adjudication Committee (AC)

In addition to the PI, two vascular neurologists will be charged with adjudicating stroke-related hospitalizations reported during the follow up period. This group (the Adjudication Committee) will review specific outcomes, including recurrent stroke, including subtype; and serious hemorrhage, including site.

C. Criteria for Intervention Discontinuation

- Revocation of informed consent.
- Subjects moving substantial distance from the original geographical location.
- Morbidity or mortality giving rise to insurmountable barriers to continued assessment.

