Study Design. C3FIT is a multicenter, randomized, single blinded, Phase III, cluster randomized trial. Sites will be stratified by patient admission volume and geographic location; subsequently, each site will be randomized to one of two patient care management strategies: the CSC/PSC versus ISPU model.

Outcomes. C3FIT’s primary outcomes are the SIS and smRS at 12 months.

Sample Size and Population. Based on the primary outcome, the study was originally designed for a total sample size of approximately 1800 patients, with approximately 18 sites. However, due to the challenges of the COVID-19 pandemic the sample size was decreased to 1,262 and the number of sites were increased to 22. The Statistical and Data Coordinating Center (SDCC) at the University of Alabama determined the change in sample size would not influence the study statistical measures and/or study power, and our funder, PCORI, approved of the changes.

Interventions. Coordinated care (including in-home/in-patient rehabilitation and skilled nursing or extended care facility visits) will be provided based on protocol-based coordination of post-acute in-home/facility care for ISPU Site patients, while CSC/PSC patients will be managed per standard CSC/PSC protocol with no additional study related management post discharge. Clinical site personnel will be provided with training specific to the arm to which they are randomized.

Duration. Patients will be followed at the site level for one year after enrollment.

1. **STUDY OBJECTIVES**

The current standard of stroke care is the JC-certified CSC/PSC care system, a collection of proven individual processes of care, but a system that lacks coordination for the post-stroke care of patients. The C3FIT trial serves as the opportunity to assess potential impact on patient QOL and functional outcomes resulting from the improved integration of care provided by the ISPU approach.

C3FIT's overall goal is to assess if patient outcomes are improved when the CSC/PSC system is supplemented with an Integrated Stroke Practice Unit (ISPU) system of care, a patient-centric model of care involving the patient and caregiver/family that coordinates care from the acute management through the rehabilitation and recovery of the patient.

A. Hypotheses

C3FIT's *Primary Hypothesis* is that the ISPU model of care will show improved mean level SIS and smRS scores at 12 months compared to the CSC/PSC model of care.

The *Secondary Hypotheses* are:

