The IPU model of care provides the coordination and integration of care not found in any other previous design. Based on a concept originally proposed by Porter and evaluated in joint replacement, spine and cancer^{26,28,29}, the IPU model incorporates components of team-based care²⁶ (i.e. coordinated care in multiple specialty areas with a specified communication mechanism, like regular in-person/ virtual team meetings²⁵), which have shown care delivery improvement²⁷ Combined with technology-enabled, home/facility-based access to multiple layers of care and more timely access to care, these represent key elements in delivering improved patient-centered outcomes. Given that caregivers also experience negative health-related QOL, engagement of both the patient and caregiver unit is also important to deliver positive outcomes^{2,8} in an IPU.

Our research group conducted a three-year, single-site pilot study as part of a CMS HCIA (#1C1CMS331043). Post-stroke care that was both integrated and coordinated showed a positive impact on long-term outcomes, as well as higher patient satisfaction and improved risk factor control⁴⁶. First devised as a NIH Office of Minority Health-funded grant in South Carolina (#CPIMP071044; PI: [name])⁴⁷ and based on the IPU concept, we implemented a stroke-specific care model called an *ISPU* (see Figure 2) that informed and largely directed design of the ISPU arm of C3FIT. This pilot ISPU included two coordinated units that addressed the entire spectrum of care, from acute assessment, diagnosis and intervention (called *Stroke Central*) through hospital discharge to 1-year post-discharge care (called *Stroke Mobile*). Stroke Central was the care coordination component that extended from acute to hospital to home/facility, impacting complications, length of stay, and readmissions. The Stroke Mobile Care Team, comprised of a Registered Nurse (RN) and a Lay Health Educator, engaged patients and caregivers in their home and/or skilled nursing or rehabilitation facility. The Stroke

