4. STUDY DESIGN

C3FIT is a randomized comparative effectiveness trial (CET) of two care delivery methodologies at approximately 18 clinical sites. Primary and secondary outcomes are described in Section 1.

A. Disease-specific Enrollment Criteria

Clinical Indicators. Definitive stroke will be defined by ICD-10 code criteria. Definitions will be based on ICD-10 criteria (see Table 4). Investigators will use tests and assessments deemed appropriate for an individual patient to determine the appropriate diagnosis. Additional stroke subtype categorization will occur using the TOAST Criteria as performed by C3FIT clinical site investigators.

Prior Therapy. There is no exclusion for prior therapy.

Demographic Characteristics. The clinical sites have been carefully selected with the goal of providing nationwide representation, urban and rural representation, inclusion of both men/women and all race/ethnic groups affected by stroke. Patients aged 18 and older are eligible with no upper age exclusion criterion.

Contraindications. Since no drugs or experimental devices are utilized in this trial there are no specific contraindications.

Pregnancy Exclusions. There is no exclusion for pregnancy or planned lactation and no inherent risk from the proposed intervention.

B. Randomization

C3FIT is randomized at the facility (clinical site) level rather than the individual patient level. Randomization at the facility level is appropriate, as the proposed comparator arms could not be reasonably instituted at the patient level for a system change design. Sites will be stratified by patient volume and geography and randomized to management using the CSC/PSC or ISPU model.

C. Site Selection

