10. HUMAN SUBJECTS PROTECTIONS

This protocol and the informed consent document (Appendix A) and any subsequent modifications will be reviewed and approved by the Steering Committee, IRB, and DSMB responsible for oversight of the study. A signed consent form will be obtained from the subjects.

The total sample size for the primary outcome for this study will be approximately 1800 patients (approximately 100 patients at each clinical site, although some sites will enroll up to 140 consented participants due to limited enrollment by other sites due to institutional COVID PANDEMIC issues) who have consented to participate.

- Participating patients at a clinical site randomized to ISPU arm will be followed by Stroke Central to collect the same acute in-hospital metrics to measure care quality, health status, and outcomes and will also be contacted via telephone by the blinded personnel at the UAB SDCC SRU to assess primary outcomes. However, ISPU patients will also be assessed monthly by Stroke Mobile for 1-year in their home to collect specific metrics that will evaluate the patient and caregiver/family for potential issues and provide follow-up care and targeted education and support.
- The patient and their caregiver (or their legally authorized representative, if patients are unable to provide consent) will be approached to participate in the study ideally during hospitalization or within 5 business days of hospital discharge ideally (to a

maximum of 14 total days) to allow for data collection of specific acute in-hospital metrics. Caregivers may be consented at any time during the C3FIT study, but no data will be collected until consent is obtained. At research visits, the following will be obtained: (1) demographic and other data collection; (2) follow-up data collection specific to the ISPU arm; and (3) contact via telephone survey to collect SIS and smRS outcome data.

- C3FIT's population will include patients with all stroke subtypes and levels of severity, regardless of gender, race, ethnicity, or socioeconomic status. Each Site will recruit from their geographically eligible patients (who have a discharge diagnosis of stroke according to their ICD-10 code) until approximately 100 patients are consented, although some sites will enroll up to 140 consented participants due to limited enrollment by other sites due to institutional COVID PANDEMIC issues.

A. Adequacy of Protection Against Risks

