Adverse events (physical, behavioral, or psychological) will be reported to the Clinical Site PI or the SDCC; they will report these adverse events per guidelines in a timely fashion to the CCC, where they will be reviewed by the PI, Project Manager and forwarded to the DSMB.

C. Potential Benefits of the Proposed Research

Benefits for Patients. The major benefit to patients will accrue to future patients who benefit from the information gained from this study to design a patient-centered stroke healthcare delivery system that is comprehensive, integrated, and caregiver/family-focused. Many of the current issues faced by stroke patients involve lack of defect free stroke care in the in-hospital phase of care, leading to longer lengths of stay and in-hospital complications. These complications can lead to loss of QOL over many years. Lack of defect free care also plagues the post-hospital phase of care where stroke recurrence leads to readmissions and less Time at Home. Patients can also benefit by access to results of C3FIT to inform their choices in health care based on data that identifies the most effective and efficient care.

Based on positive results of C3FIT, patients could also benefit by having the potential for home care management, avoiding time and travel costs for outpatient clinic visits. Patients will have screening for HbA1C and cholesterol to measure risk factor control at-target which may help identify targets of therapy. Patients could also benefit by having their caregivers supported by study personnel reducing caregiver strain. Because patients are involved in the design, implementation and dissemination of C3FIT outcomes that matter to them will be foremost in the study design.

Benefits for Caregivers. The major benefit to caregivers will accrue to future caregivers where the information gained from this study can be used to design a patient-centered stroke healthcare delivery system that is comprehensive, integrated, and caregiver/family-focused. Such a system may encourage recovery in their associated patient and limit stroke recurrences and readmissions.

If results from C3FIT are positive, caregivers could have the potential advantage of home visits, avoiding the stress, time commitment, and travel costs of clinic visits. Caregivers could potentially benefit by having a team that monitors their stress level and offers support.

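### The PI reviews adverse events and also sits on the Adjudication Committee, and no adjudicator is described as masked to site or arm, which exposes recurrent stroke, a secondary outcome

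*Protocol*

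**What the plan says.** The two arm-specific versions of the protocol (ISPU and CSC/PSC) carry the same text on this point.

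- **Membership (Section 8.B):** "In addition to the PI, two vascular neurologists will be charged with adjudicating stroke-related hospitalizations reported during the follow up period". The group "will review specific outcomes, including recurrent stroke, including subtype; and serious hemorrhage, including site".
- **Adverse events (end of Section 10.B):** "Adverse events (physical, behavioral, or psychological) will be reported to the Clinical Site PI or the SDCC". They then pass to the Clinical Coordinating Center (CCC), "where they will be reviewed by the PI, Project Manager and forwarded to the DSMB".
- **Unit of randomization (Section 4.B):** "C3FIT is randomized at the facility (clinical site) level rather than the individual patient level".
- **Blinding (Summary):** "C3FIT is a multicenter, randomized, single blinded, Phase III, cluster randomized trial". Who is blinded is not defined there. Section 10 names one group, the coordinating center's Survey Research Unit (SRU): participants are "contacted via telephone by the blinded personnel at the UAB SDCC SRU to assess primary outcomes".
- **Analysis (SAP 4.1):** days from discharge to recurrent stroke are compared by hierarchical proportional hazards. The SAP does not say whether the event is the one a site reports or the one the committee confirms.

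**The concern.** Whether new symptoms in a recent stroke patient are a recurrence, a worsening of the index deficit or something else is a matter of judgement. A reader who knows the arm can lean one way on unclear cases without intending to. Adjusting for severity, demographics or risk factors cannot remove that error, because arm is its source.

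Two features of this trial make the adjudication step matter more than usual. Recurrence surveillance is monthly in the ISPU arm but takes place only at months 3, 6 and 12 in the CSC/PSC arm (Table 7 of each version), so suspected events may reach the committee at different rates. Adjudication is then the main filter common to both arms. SAP 4.1 also expects that recurrent strokes may be few, so a handful of reclassified cases could move the estimate.

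**Working it through.** The plan gives no figure to reproduce. The check sets the relevant statements side by side.

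1. **Does the PI adjudicate?** Yes. Section 8.B says so in both versions.
2. **Does the PI also review adverse events?** Yes. Section 10.B says so in both versions and states no exception.
3. **Is it the same person?** Very likely. Section 10.B separates the Clinical Site PI from the PI, and its list of participant protections counts the C3FIT PI among CCC staff. The documents do not say so outright.
4. **Does that person know the arm?** Almost certainly. Arm is fixed by site (Section 4.B), site training is specific to the arm (Summary), and the CCC monitors intervention delivery site by site (ISPU version, Section 5).
5. **Is any adjudicator masked?** None is described as such. Table 1 has medical records come from the site to the committee when needed. Section 10.F identifies records that leave the site by study number only, to protect confidentiality. That hides the patient, but nothing says that it hides the hospital.
6. **Which analyzed outcomes depend on the verdict?** Only recurrent stroke, and only if SAP 4.1 means adjudicated events. Serious hemorrhage is adjudicated and watched by the DSMB but is not an outcome in Protocol Section 1.B or the SAP. SIS and smRS come from SRU calls. Death, scored 6 on the mRS in SAP 3.2, is a matter of fact rather than judgement.

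**Scale.** The share of unclear cases, and how far knowledge of arm would move them, are not in the documents, so no bias can be computed. What can be shown is how much one case weighs. Assume the reduced target of 1,262 patients, an even split of events between arms, full follow-up and no clustering. Let the recurrence rate run from an assumed 5% up to the 20% at 90 days quoted in the protocol's Table 3.

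- Events: 0.05 × 1,262 ≈ 63; 0.20 × 1,262 ≈ 252.
- Removing one event from one arm changes an event ratio of 1.00 to 30.5/31.5 = 0.97 with 63 events, or 125/126 = 0.99 with 252.
- Standard error of the log hazard ratio ≈ 2/√events: 2/√63 = 0.252; 2/√252 = 0.126.
- 95% limits, as a factor each way: exp(1.96 × 0.252) ≈ 1.64; exp(1.96 × 0.126) ≈ 1.28.

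Each reclassified case would thus shift the ratio by about 1% to 3%, against random error of roughly 28% to 64%.

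**The case against.** The strongest reply is that silence is not evidence of unmasked adjudication. A charter outside these documents may specify redacted packets. The primary outcomes are protected, the exposed outcome is secondary, and random error would be large beside a few reclassified cases. All of that stands, and it limits the weight of the point. It does not remove it, because the PI's membership is a stated rule and not a missing detail.

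Several stronger readings are tempting, but the documents do not support them:

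- *The PI has already seen every case unmasked before adjudicating it.* Section 10.B gives no order of events and does not mention masking. Recurrences are also picked up by visit surveillance, so they need not arrive through adverse event reports.
- *The PI holds one of three votes.* No voting or consensus rule is given.
- *The PI has a stake in the result.* Section 2.B says of the pilot work: "we implemented a stroke-specific care model called an *ISPU* (see Figure 2) that informed and largely directed design of the ISPU arm of C3FIT". It attributes that work to the research group, and nothing states that the PI in Section 8.B led it.
- *Adjudication packets contain Stroke Mobile notes.* Table 8 lists teleconsult documentation as study data. Nothing says that it goes to the committee.
- *Hemorrhage results are biased.* The SAP analyzes no hemorrhage outcome.
- *The damage cannot be undone.* Stored records could be redacted and read again, and site-reported events could be analyzed alongside.

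**Conclusion.** The point holds as a cheap improvement to a secondary outcome. The plan seats as an adjudicator someone who almost certainly knows the arm, describes no masking for any of the three, and leaves open whether the committee's verdict or the site's report is analyzed. Time to first recurrent stroke is exposed; SIS and smRS are not. The size and direction of any bias are unknown.

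This rests on three assumptions: that Sections 8.B and 10.B mean the same PI, that no separate charter already masks the adjudicators, and that adjudicated events feed SAP 4.1. If a charter does specify masking, the remaining work is to cite it and complete SAP 4.1.

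**What to change.** **Protocol 8.B, both versions.** State that the two vascular neurologists adjudicate recurrent stroke independently, from packets in which the Statistical and Data Coordinating Center has removed site and arm-identifying text. The PI has no vote and keeps the adverse event review in Section 10.B. Disagreements go to a joint masked re-read. Because two readers may still differ, write down a default for unresolved cases in advance.

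**SAP 4.1.** Define recurrent stroke as the masked adjudicated event, and add an analysis of site-reported events as a sensitivity analysis.

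**If adjudication is complete.** The SAP introduction already speaks of 21 sites that provided data, so a change to the protocol may come too late to act prospectively. In that case, apply the same rules as a masked re-read of the stored records.

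**Cost.** Redaction work, occasional joint re-reads and a few sentences of text. No new adjudicator is needed.
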